4.2 SCIENTIFIC RATIONALE FOR STUDY DESIGN

Determining the clearance (Cl/F) and volume of distribution (V_d/F) of each of the major kavalactones will allow us to determine the optimal dosing regimen to maximize the pharmacodynamics and optimize compliance.

4.3 JUSTIFICATION FOR DOSE

We have isolated the major chemicals in kava and determined their benefits (66) and risks (32) in vivo. With such knowledge, we screened twenty-five commercially available kava products and quantified the major beneficial kavalactones, including kavain, dihydrokavain, methysticin, and dihydromethysticin (DHM, the chemopreventive ingredient), and the hepatotoxic compounds – flavokavains A and B (30). We identified one dietary kava product from Gaia Herbs (Kava Root) for our pilot human trial that has a high DHM content and low flavokavain A and B content. To ensure consistency, we characterized the content of three batches of this product by HPLC and NMR. Each capsule contained 75 \pm 3 mg of kavalactones (the anxiolytic ingredients), consistent with the labeled 75 mg kavalactone per capsule. Each capsule also contained ~20 mg DHM. With three capsules per day, the human daily dose of kava is within the proposed anxiolytic range (120-280 mg daily (14)); the amount of DHM would be comparable

A Phased Clinical Trial of a Dietary Supplement Kava: Biomarker Changes and Anxiolytic Effects Phase 1: Kava Pharmacokinetics

Version 5.000

Protocol PAR-18-829 11 May 2021

to its in vivo chemopreventive dose. This kava product also contained minimal flavokavains A and B (<1.0 mg/capsule).

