
varied by 10 – 30 fold (30) despite the fact that these kavalactones have been recommended for standardization (48). These products therefore likely vary significantly in their anxiolytic efficacies. The abundance of the hepatotoxic compounds, flavokavains A and B (32), varies even more (30), such that some products may impose higher risk of hepatotoxicity than others. Rigorous research therefore is needed to characterize kava's pharmacology in conjunction with accurate characterization of its chemical compositions, essential to maximize kava's benefit and to minimize its potential adverse risk. Kava is safe for use in clinical populations, especially when properly prepared. Kava was banned for clinical use in Europe from 2001 – 2014 because of concerns about potential hepatotoxicity (26). However, the purported incidence rate of kava-induced hepatotoxicity is extremely low (0.3 - 1) cases per one million daily doses) (48-56), much lower than BZD-based anxiolytics (57, 58). In addition, the WHO found that kava-related hepatotoxicity was likely due to quality problems, adulteration of the root with other parts of the plant, use of ethanol- rather than water-based extraction, and in some cases, interactions between kava and other drugs/herb preparations or chronic alcohol use (5, 49, 50, 59). As a result of these assessments, the ban on kava use was lifted in 2014, and kava is again available for use in Europe (26). We have closely monitored the safety of kava and its ingredients in all of our studies. We detected no signs of hepatotoxicity when kava was evaluated alone, even at elevated dosages and extended exposures (27-29, 32, 36, 60, 61). This was further supported by the results of our recent study, demonstrating that kava was safe unless co-administered with acetaminophen, due to flavokavains A and B (32), two lipophilic chemicals low in aqueous extracts (30). This finding suggests that the already low rate of potential hepatotoxicity with kava can be further mitigated by the use of preparations that have low (or no) levels of flavokavains A and B, and by excluding patients who are taking medications known to have potential hepatotoxicity. The risk of observing an instance of hepatotoxicity according to the WHO is less than 0.03% in the R61 phase and less than 0.9% in the R33 phase of this study; this risk is further mitigated by our use of flavokavain A/B-free kava.

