2.3.1 KNOWN POTENTIAL RISKS

The risks of participating in this project include those incurred during the administration of rating scales, blood drawing, and the administration of study medication (kava).

Drawing blood requires venipuncture and is associated with the momentary discomfort of the needle stick. The risks of venipuncture include discomfort at the site of puncture, possible bruising and swelling around the puncture site, rarely an infection and uncommonly faintness.

Potential side effects from the administration of Kava include: excessive sedation if combined with alcohol, rare allergic reactions and rare liver toxicity. The frequency of liver injury in Kava is not known. Based upon reported cases, liver injury due to kava is less than 1:1,000,000 daily doses, and is likely due to the presence of flavokavains A and B in the kava preparation. A few cases of clinically apparent liver injury have been published in the literature. One of the potential risks with kava is an acute liver injury with severe hepatitis ending in fulminant hepatic failure, requiring liver transplantation, or even leading to death. Preliminary data from a previous human study by our group did not identify any adverse events due to the consumption of kava supplementation. In addition, we

Protocol PAR-18-829 11 May 2021

are using a kava preparation that has been rigorously tested for the removal of flavokavains A and B, which are thought to cause the rare cases of liver toxicity that have been observed.

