6.2.2 FORMULATION, APPEARANCE, PACKAGING, AND LABELING

Bottles of flavokavain AB-free kava (75 mg kavalactones/capsule) with the same lot number will be directly purchased from Thorne Research Inc. This product will be used because of its lack of flavokavains A and B (<0.2 mg/capsule) and consistent content of total kavalactones. For ongoing quality control, three capsules from each bottle will be analyzed via our established method to ensure adequate and constant content of total kavalactones and no flavokavains A and B. The Investigational Drug Service (IDS) pharmacy will package the investigational kava. Supplies with the appropriate number of capsules for each subject will be prepared and bottled for administration.

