6.2.4 PREPARATION

Bottles of flavokavain AB-free kava (75 mg kavalactones/capsule) with the same lot number will be directly purchased from Thorne Research Inc. This product will be used because of its lack of flavokavains A and B (<0.2 mg/capsule) and consistent content of total kavalactones.

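### Does it matter that the dose justification describes a different manufacturer's kava product from the one given to participants?

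*Combined protocol and SAP*

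**What the plan says.** Section 4.3 (Justification for Dose) reports finished work on a commercial product: "We identified one dietary kava product from Gaia Herbs (Kava Root) for our pilot human trial". Three batches were assayed. The section gives 75 ± 3 mg kavalactones and less than 1.0 mg flavokavains A and B per capsule, and for dihydromethysticin (DHM), "Each capsule also contained ~20 mg DHM". It then argues that three capsules a day fall within a proposed anxiolytic range of 120-280 mg, and that "the amount of DHM would be comparable" to a chemopreventive dose found in vivo.

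Sections 6.2.2 and 6.2.4 specify what participants receive. Bottles from a single lot, labelled at 75 mg kavalactones per capsule, "will be directly purchased from Thorne Research Inc". Both sections give the reason: "This product will be used because of its lack of flavokavains A and B (<0.2 mg/capsule) and consistent content of total kavalactones". Section 6.2.2 adds an assay of three capsules from each bottle, for total kavalactones and for absence of flavokavains A and B. Section 6.2.1 gives the daily total as 225 mg.

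Section 4.3 does not mention the purchased product, and no other section connects the two.

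**The concern.** A dose justification should describe what is given. Here the composition figures belong to another manufacturer's capsule, and the reader is not told. The phrase about a pilot human trial does not settle the matter, because Sections 1.1, 4.1 and 9.2 call the present study a pilot as well. On one reading, 4.3 borrows data from an earlier study without saying so. On the other, 4.3 and 6.2.2 disagree about the study product.

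The protocol itself gives a reason for care. Section 2.2 says that across 25 commercial products the abundance of the major kavalactones "varied by 10 – 30 fold (30) despite the fact that these kavalactones have been recommended for standardization", so one product's DHM content cannot be assumed for another. The objective in Section 3 and the liver-risk text in Sections 2.3.1 and 2.3.3 also rely on a product from which flavokavains A and B have been removed, and the limit in 4.3 is looser than that in 6.2.2.

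Two things could be at stake: the support for the dose, and the dose input for apparent clearance (Cl/F) and apparent volume (Vd/F) of each kavalactone, which Section 4.2 wants in order to choose a regimen.

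**Working it through.** **Inputs.** Section 4.3 product, per capsule: 75 ± 3 mg kavalactones, about 20 mg DHM, <1.0 mg flavokavains A and B. Dosed product (6.2.2, 6.2.4), per capsule: 75 mg kavalactones, <0.2 mg flavokavains A and B, DHM not stated. Three capsules per participant (4.1, 6.1.2).

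**1. Total dose.** The plan's own figure reproduces: 3 × 75 = 225 mg. It is the same for both products. At 75 ± 3 mg the 4.3 product spans 3 × 72 = 216 mg to 3 × 78 = 234 mg. All of these lie inside 120-280 mg.

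**2. Flavokavains A and B.**

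| | Per capsule | Three capsules |
|---|---|---|
| Section 4.3 product | <1.0 mg | <3.0 mg |
| Dosed product | <0.2 mg | <0.6 mg |

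The limits differ by 1.0 / 0.2 = 5. These are upper limits, not measured contents. Anything below 0.2 mg is also below 1.0 mg, so the 4.3 statement remains true of the dosed capsule. A reader who relied on 4.3 alone would overstate the limit for the dosed product.

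**3. DHM.** The 4.3 product gives 3 × 20 = about 60 mg. No figure can be computed for the dosed capsule. The 10-30 fold spread in Section 2.2 is across 25 products and does not estimate the gap between these two.

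**4. Half-life.** Suppose the analyst entered a kavalactone dose that was *k* times the true one. For DHM, taking 20 mg when the dosed capsule holds *d* mg gives *k* = 20/*d*. The plasma concentrations are as observed, so under linear kinetics both apparent parameters scale together:

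- Cl/F entered = *k* × Cl/F true
- Vd/F entered = *k* × Vd/F true
- half-life (one-compartment form) = ln 2 × (*k* × Vd/F) / (*k* × Cl/F) = ln 2 × (Vd/F) / (Cl/F)

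The factor cancels. With more compartments, the rate constants are likewise ratios of clearances to volumes, so the same holds. All capsules come from one lot, so *k* is common to all participants and the model fit is unchanged. The primary endpoint is therefore unaffected even by a wrong dose input.

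**5. Cl/F and Vd/F.** These would be wrong by the factor *k*, so the content of each kavalactone in the dosed lot does matter for them. But Section 9.4.1 names no dose source, and no text directs the analyst to 4.3. DHM is also the only individual kavalactone for which 4.3 gives an amount, so that section could not supply the inputs for six kavalactones in any case.

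**The case for a change.** The best case for a change is that the problem survives either reading of the pilot wording. The text of 4.3 leaves the past tense where it argues for the dose, and three capsules is this study's regimen, so a reader will apply those sentences to it. The only per-capsule amount of a single kavalactone in the whole document belongs to the other product. The repair would take a sentence or two.

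The facts stand: the manufacturers differ, 4.3 is silent about it, and the DHM comparison has no support for the dosed capsule. The consequence does not follow. Section 4.3 most naturally recounts earlier work. It reports completed assays on a product chosen for high DHM, which it calls the chemopreventive ingredient, whereas this protocol concerns anxiolysis. Section 2.3.1 confirms that earlier work existed: "Preliminary data from a previous human study by our group did not identify any adverse events due to the consumption of kava supplementation". The operational sections state unambiguously what is bought and why. No objective or endpoint in Section 3 concerns chemoprevention.

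The dose-input point has more substance, but it is separate from the labelling of 4.3. The capsule assay in 6.2.2 is specified for total kavalactones and flavokavains only, so it cannot be assumed to deliver the content of each kavalactone. Sections 2.2 and 4.3 do show that the group has measured individual kavalactones in commercial products. An analyst fitting each one separately cannot run the model without its dose and would have to obtain it for the lot dosed.

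**Conclusion.** No change to the plan is called for. The discrepancy between 4.3 and 6.2.2/6.2.4 is a clerical one in background text. It alters neither the 225 mg total, nor its place within 120-280 mg, nor the half-life endpoint, and the dosed product meets a flavokavain limit five times tighter than the one 4.3 quotes. The sole unsupported statement is the DHM comparison, which nothing in this study uses. Labelling the 4.3 figures as the other product's would be tidier, but it would change no procedure, analysis or result.

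This rests on three assumptions: that 6.2.2 and 6.2.4 describe what is actually dispensed, that kinetics are linear over the dose given (needed for the cancellation shown above), and that Cl/F and Vd/F are computed from the content of the lot dosed. The documents do not state the third, but they contain nothing against it.

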4.4 END OF STUDY DEFINITION

The study will come to an end when the data for 10 healthy subjects has been collected and analyzed.

5 STUDY POPULATION

Protocol PAR-18-829

5.1 INCLUSION CRITERIA

All subjects must meet the following criteria at baseline to be eligible for participation in the pharmacokinetic study:

- Be between the ages of 18 and 50 years
- Females of potential childbearing status must use adequate contraceptive precautions.

5.2 EXCLUSION CRITERIA

Subjects will be excluded if they meet any of the following criteria at the time of screening or at their baseline visit:

- Currently taking any medication or supplement other than vitamins
- Inability to refrain from acetaminophen, alcohol, or other potentially hepatotoxic substances during the study
- Have a history of liver disease or currently have liver disease. (d) Elevation in serum ALT, AST, ALP or total
 bilirubin that reaches clinical significance (as determined by the PI) at screening. Have an unstable
 medical, psychiatric, or neurological condition determined by history taken during the screening visit and
 a physical examination at the baseline visit.
- Have a positive urine drug screen for substances of abuse.
- Current tobacco users will be excluded.

5.3 LIFESTYLE CONSIDERATIONS

This study will exclude any individual who is a current tobacco smoker and anyone who is not able to abstain from alcohol consumption for the duration of the study.

5.4 SCREEN FAILURES

Subjects who do not meet inclusion and/or meets criteria for any of the exclusion criteria will be deemed a screen fail.

5.5 STRATEGIES FOR RECRUITMENT AND RETENTION

We will recruit and screen potential participants until we are able to randomize and enroll 10 healthy individuals in the R61 pk phase trial. We will recruit males and females of all races/ethnicities ages 18-50 from the following locations.

Recruitment sites will include:

Protocol PAR-18-829

Gainesville and the surrounding community: Gainesville has a population of approximately 100,000 people, not including the student population. Alachua County, which includes Gainesville and the surrounding towns and rural areas, has a population of over 250,000 residents

6 STUDY INTERVENTION

6.1 STUDY INTERVENTION(S) ADMINISTRATION

6.1.1 STUDY INTERVENTION DESCRIPTION

Participants will be asked to refrain from food, liquids other than water, and medications for 12 hours prior to entering the Clinical Research Center of the UF CTSI. They will have an indwelling venous catheter placed in the lower arm to facilitate the multiple blood collections during the study (Support Letter from CTSI and its quote of estimated cost attached in Appendix). Each subject will take three 75 mg kava capsules and ten blood draws (2 mL EDTA vacutainer) will be collected corresponding to the absorption, distribution, metabolism and excretion phase of the pharmacokinetic curve. Specifically, blood will be withdrawn at baseline and 0.5, 1, 2, 3, 4, 5, 6, 8 and 12 hours after kava ingestion, based on our mouse pharmacokinetic knowledge of kava. The blood samples will be processed and then stored at -80°C till analysis. The period of follow up for any delayed adverse effects (e.g, monitoring of liver function) will be extended such that all participants will be followed for a full 12 weeks after their last kava ingestion.

6.1.2 DOSING AND ADMINISTRATION

Each subject will take three 75 mg kava capsules and 10 blood draws (2 mL EDTA vacutainer) will be collected corresponding to the absorption, distribution, metabolism and excretion phase of the pharmacokinetic curve

6.2 PREPARATION/HANDLING/STORAGE/ACCOUNTABILITY

6.2.1 ACQUISITION AND ACCOUNTABILITY

Subjects will be provided with either a onetime dosage or a three time dose of kava (each capsule being 75mgs for a total of 225 mgs for a daily total dose) at the baseline visit. Ingestion of kava will be monitored by the research coordinator and documented on a study drug accountability log.

6.2.2 FORMULATION, APPEARANCE, PACKAGING, AND LABELING

Bottles of flavokavain AB-free kava (75 mg kavalactones/capsule) with the same lot number will be directly purchased from Thorne Research Inc. This product will be used because of its lack of flavokavains A and B (<0.2 mg/capsule) and consistent content of total kavalactones. For ongoing quality control, three capsules from each bottle will be analyzed via our established method to ensure adequate and constant content of total kavalactones and no flavokavains A and B. The Investigational Drug Service (IDS) pharmacy will package the investigational kava. Supplies with the appropriate number of capsules for each subject will be prepared and bottled for administration.

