3 OBJECTIVES AND ENDPOINTS

| OBJECTIVES | ENDPOINTS | JUSTIFICATION FOR ENDPOINTS |
|---|--|---|
| Primary | | |
| To characterize pharmacokinetics of flavokavain A/B-free kava | Examining the half-life of each of the six major kavalactones | This is a standard marker for pharmacokinetics studies |
| Secondary | | |
| None | None | N/A |
| Tertiary/Exploratory | | |
| To characterize plasma cortisol level upon A/B-free kava use | Validate the method and provide pharmacodynamic knowledge of kava on plasma cortisol, which is a biomarker candidate for the biomarker phase of this study | The results will support the studies proposed in the biomarker phase of this study. |

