6.2.3 PRODUCT STORAGE AND STABILITY

Product will be stored according to manufacturer recommendations. All unused supplement will be returned to IDS via study personnel and destroyed by IDS.

Protocol PAR-18-829

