9.4 STATISTICAL ANALYSES

9.4.1 GENERAL APPROACH

Plasma concentration-time data of individual kava lactone in will be subjected to non-linear mixed effect modeling (NONMEM). Compartmental modeling approach will be applied to achieve the best fit model on the basis of residual sum of squared error, Akaike's Information Criterion and objective function value. Chi-squared distribution will be assessed to evaluate the significance; e.g. an objective function change (OBJ) of 3.84 is significant at alpha=0.05.

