9.4.2 ANALYSIS OF THE PRIMARY EFFICACY ENDPOINT(S)

Pharmacokinetic parameters will be derived from this study and these parameters will be used to design future efficacy studies

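### Must the plan state the milligrams of each kavalactone in the trial capsules before it can estimate Cl/F and Vd/F for each compound?

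*Combined protocol and SAP*

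**What the plan says.** Three parts of the protocol bear on this.

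- **What is to be estimated.** The only primary endpoint, in section 3, is "Examining the half-life of each of the six major kavalactones". Section 4.2 goes further and rests the choice of regimen on "Determining the clearance (Cl/F) and volume of distribution (V_d/F) of each of the major kavalactones". Section 9.4.1 takes "Plasma concentration-time data of individual kava lactone" as the unit of modelling in NONMEM, and 9.4.2 adds that "these parameters will be used to design future efficacy studies".
- **What is known about the trial product.** Sections 6.2.2 and 6.2.4 describe one lot from one named supplier, labelled 75 mg kavalactones per capsule, with less than 0.2 mg of flavokavains A and B. Section 6.2.1 gives a total of 225 mg per participant. For quality control, three capsules per bottle are "analyzed via our established method to ensure adequate and constant content of total kavalactones and no flavokavains A and B".
- **The only amount given for a single compound.** Section 4.3 reports that "Each capsule also contained ~20 mg DHM", but that sentence describes another supplier's product, used in an earlier pilot trial.

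No section gives the content of each kavalactone in the trial lot, and 9.4.1 does not name the dose each model will use.

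**The concern.** Apparent clearance is dose divided by exposure. With six separate models there must be six separate doses, and the plan writes down only their sum. A stable total does not fix the split between compounds. Section 2.2 reports that the major kavalactones varied 10- to 30-fold across 25 commercial products, so one product's composition cannot be assumed for another.

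If the wrong dose were entered, Cl/F and Vd/F would be wrong by the same factor, and by a different factor for each compound. That would spoil comparisons between compounds and any use of the values for material of different composition. Section 9.4.2 says the parameters will serve later studies and does not say those studies will use this lot. Section 6.2.3 also says "All unused supplement will be returned to IDS via study personnel and destroyed by IDS", which suggests that an amount not recorded at the time might be lost.

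**Working it through.** **Total dose.** 3 capsules × 75 mg = 225 mg, which reproduces the figure in 6.2.1.

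**How a dose error carries through.** For compound *i* with true dose D and exposure AUC:

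- Cl/F = D / AUC
- Vd/F = (Cl/F) / k, where k is the elimination rate constant, taken from the slope of the curve
- t½ = ln 2 × (Vd/F) / (Cl/F) = ln 2 / k

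If the analyst enters r × D instead of D, Cl/F and Vd/F are both multiplied by r. In t½ the factor r cancels.

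**Numerical check.** Assume a true dose of 60 mg, Cl/F = 100 L/h and Vd/F = 400 L. Then AUC = 60/100 = 0.6 and k = 100/400 = 0.25 per hour. These values only exercise the algebra and do not describe the trial product.

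| Dose entered | Cl/F | Vd/F | Reported/true | t½ |
|---|---|---|---|---|
| 37.5 mg (225/6, equal split) | 37.5/0.6 = 62.5 | 62.5/0.25 = 250 | 0.625 | 2.773 h |
| 60 mg (true) | 60/0.6 = 100 | 100/0.25 = 400 | 1.00 | 2.773 h |
| 225 mg (total used) | 225/0.6 = 375 | 375/0.25 = 1500 | 3.75 | 2.773 h |

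**Same-lot predictions.** For n capsules of the same lot, predicted AUC = (n/3 × rD) / (r × Cl/F). The factor r cancels, so exposure at any number of these capsules is predicted correctly.

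**Comparisons between participants.** All bottles carry one lot number, so r is the same for everyone, apart from capsule-to-capsule variation. It therefore cancels in the ratio of one participant's Cl/F to another's. The CYP2D6 question in 4.1 compares participants in this way and is not disturbed.

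**What does depend on r.** Absolute Cl/F and Vd/F, ratios between compounds, and predictions for a lot of different composition (off by 1/r). If the 225 mg total were entered for every compound, r would be 1/share. Over an assumed range of shares from 40% to 5%, that is 1/0.40 = 2.5 to 1/0.05 = 20. These are the consequences of a specific mistake. No passage says or implies that the team would make it.

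**Whether the right figure is available.** Section 2.2 describes LC-MS/MS analysis of 25 products that gave the abundance of the major kavalactones. Section 4.3 reports both a total and a DHM amount per capsule for the pilot product. The primary endpoint itself requires six kavalactones to be measured separately in plasma. The group can therefore resolve individual compounds, and three capsules from every bottle are already on the bench.

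**The case for a change.** The strongest case for a change is that the plan promises more than half-life. Sections 4.1, 4.2 and 9.4.2 all look ahead to dosing decisions, and 2.2 itself asks for pharmacology to be studied together with accurate chemical composition. Writing the commitment down would cost almost nothing, since no extra capsules are needed, and the text as it stands does not rule out entering the total.

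Part of this stands. The sentence is missing, and absolute Cl/F and Vd/F cannot be interpreted until someone supplies the content of each compound. Section 4.3 openly attributes its DHM figure to the pilot product, so that figure cannot fill the gap.

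The rest is weaker. The 10- to 30-fold spread is between commercial products and may partly reflect total strength. It does not measure variation between lots of one product. Disposal under 6.2.3 concerns leftover capsules, not assay results, and 10.1.9.2 provides for records to be retained. The large error factors need the analyst to enter a total, or another supplier's content, as the dose of a single compound. A pharmacokineticist fitting one model per compound has to supply a dose for that compound, and the trial's own capsule assay is the obvious source.

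One uncertainty remains on the other side. Section 4.3 names only four kavalactones and the six are never listed, so it is an inference that the capsule assay covers all six.

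**Conclusion.** No change follows. The plan omits a detail of execution that the analysis forces someone to supply and that the planned assay is well placed to give. The error in half-life is zero for any dose entered, and so is the error in same-lot predictions. The error in absolute Cl/F and Vd/F equals the ratio of entered to true content. With the assayed content as input, that ratio should be close to 1, limited by assay error and capsule variation. The documents do not allow a firmer figure, because the composition of the trial lot is not stated.

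This rests on three assumptions: the capsule assay resolves individual kavalactones as the group's earlier work did; all participants receive the one lot described in 6.2.2; and the modeller uses the assayed content rather than the label total. If the first failed, absolute Cl/F and Vd/F would have to be reported as unknown up to a scale factor, but the primary endpoint would still stand. For a 10-person pilot that 9.2 describes as preliminary, that is a modest exposure.
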